#### 8.5 Stopping Rules

The following findings will trigger a temporary halt in enrollment and administration of the product to new subject pending a safety review:

- Allergic reaction after product administration which resulted in severe anaphylactic reaction
- Occurrence of a severe cardiovascular event or pulmonary embolism in a minimum of two patients as evidenced by clinical and CT findings

•

#### 8.6 Data Safety and Monitoring Board (DSMB)

An independent DSMB appointed by the Sponsor will review the protocol and will thereafter provide medical and ethical guidance related to the conduct of this trial. During the study, the board will conduct ongoing review of the nature, frequency and severity of safety data. The DSMB Chairperson has the option to recommend suspension of enrollment in the study if, upon initial deliberation by the DSMB, urgent safety issues or alarming trends in summary safety data are identified that require further investigation.

The study sponsor will report all serious adverse events to the study DSMB. The DSMB will determine whether enrollment will be continued, suspended, or terminated. In the event that the DSMB determines that the study will be suspended or terminated, the study sponsor will notify the Institutional Review Boards and the appropriate regulatory agencies.

## 9 STATISTICAL CONSIDERATIONS

Statistical analyses will be descriptive. Summary statistics will consist of sample size (N), means, standard deviations, medians, and minimum and maximum values for continuous variables, and counts and percentages for categorical variables. Tables will summarize all safety and efficacy outcome measures by actual treatment received. Summary tables will indicate the number of subjects with complete data for each measurement, event or outcome. No substitutions will be made for missing data. All analyses will be based on available data.

A detailed Statistical Analysis Plan will be written prior to data analysis. Significant deviations from the original statistical analysis plan will be detailed in the final study report.

#### 9.1 Randomization

Once eligibility and consent are confirmed, participants will be randomly assigned to the experimental or placebo group in a 1:1 allocation ratio, stratified by site. At 90 days the two groups will change arms and the placebo group will receive the stem cell infusion and the initially treated group will receive a LRS at a volume of 1 mL/kg.

#### 9.2 Primary Safety Analysis

All safety outcomes will be summarized in tables and listings presented by experimental group. Continuous measures will be summarized with descriptive statistics (N, mean, SD, median, min, max). Categorical measures will be summarized using counts and percentages. The incidence of adverse events will be presented by toxicity grade, MedDRA system organ class and preferred term, and by relationship of the adverse events to the study treatment and compared using a Fisher's Exact Test. Laboratory and vital signs data will be presented using shift tables and summaries of change from baseline to the maximum post-administration value and compared using analysis of covariance (ANCOVA) models.

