#### **STUDY DESIGN**

This is a Phase IIa, single blind, placebo-controlled, crossover, multi-center, randomized study in subjects with NIHF. The study will enroll 20 subjects and will consist of 2 cohorts. Enrolled subjects will be randomized at 1:1 into an experimental group (n=10) or a placebo group (n=10), respectively. Subjects in the experimental group will receive 1.5 million cells per kg and subjects in the placebo group will receive 1 mL/kg Lactated Ringer's Solution. At 90 days the two groups will change arms and the placebo group will receive 1.5 million cells per kg and the initially treated group will receive a Lactated Ringer's Solution (LRS) at a volume of 1 mL/kg.

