## STUDY ENDPOINTS

#### **PRIMARY ENDPOINT**

#### Safety

Baseline and days 30, 60, and 90 post-initial infusion. After the crossover phase all patients will be evaluated at days 30, 60, and 90 days post the new infusion

- 1. Procedural complications
- 2. Vital signs
  - a. Temperature
  - b. Systolic blood pressure/diastolic blood pressure
  - c. Heart rate
  - d. Respiratory rate
  - e. Weight
- 3. Changes in heart failure medications
- 4. Clinical arrhythmias, defibrillator firing and anti-tachycardia pacing
- 5. Laboratory tests
  - a. CBC/PLT/differential
  - b. Chemistry-12, including liver function tests
  - c. Creatinine kinase
  - d. Troponin-I
- 6. Electrocardiogram
- 7. Composite of all-cause mortality all-cause admission and need for co-intervention. E.g. IV diuretics for worsening heart failure (RADIENCE trial criteria).

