## SECONDARY ENDPOINT

#### Efficacy

Change in LVEF from baseline to day 90 post initial infusion. After the crossover phase all patients will be evaluated for change from the new baseline (day 90 after the initial phase) to day 90 post new infusion.

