## STATISTICAL METHODS

All randomized subjects who receive at least part of a dose of aMBMC or LRS will be included in the safety analysis. Subject safety data will be analyzed by actual dose level (i.e., number of cells/kg). Adverse events will be coded according to the MedDRA adverse event dictionary. The results will be tabulated to examine their frequency, affected organ systems, severity and relationship to study stem cell administration. The results of laboratory tests will be similarly evaluated. The efficacy analyses will include subjects that received the full dose of aMBMC or LRS and have the appropriate follow-up completed at the scheduled assessments (i.e., efficacy evaluable population). Safety measures include the composite of all-cause mortality, admission for worsening HF and all-cause admissions. Measurement of left ventricle end diastolic volume, left ventricle end systolic volume, left ventricular ejection fraction (LVEF), longitudinal strain and strain rate, global and segmental strain and strain rate, exercise capacity by 6 minute walk distance test, biomarkers, Kansas City Cardiomyopathy Questionnaire (KCCQ) and the New York Heart Association (NYHA) Classification will be completed in the entire efficacy evaluable population. A formal statistical analysis plan will be conducted in accordance with the guidelines of Good Clinical Practice (GCP), including the archiving of essential documents.

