## 8.2.1 Adverse Event Reporting Period

The study period during which all AEs and SAEs must be reported begins after initiation of study treatment and ends at study completion or study discontinuation/termination, whichever is earlier. Any condition present between consenting and time of treatment will be considered as baseline and not recorded as an AE. After this period, investigators should report only SAEs that are attributed to study treatment.

All AEs that are observed or reported prior to initiation of study treatment will be recorded as unrelated to treatment and those occurring after initiation of treatment will be recorded as treatment-emergent.

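### Section 9.2 labels the safety groups differently from the rest of the plan, does not say which period enters the Fisher and ANCOVA comparisons after the Day 90 crossover, and tests laboratory and vital-sign change only to the maximum

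*Combined protocol and SAP*

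**What the plan says.** **Grouping.** Section 9.2 states: "All safety outcomes will be summarized in tables and listings presented by experimental group". Under Study Design in the Synopsis the same term names one randomised arm: "Enrolled subjects will be randomized at 1:1 into an experimental group (n=10) or a placebo group (n=10), respectively". The introduction to Section 9 says: "Tables will summarize all safety and efficacy outcome measures by actual treatment received". Statistical Methods in the Synopsis analyses safety by actual dose level in cells per kg, and sets the population: "All randomized subjects who receive at least part of a dose of aMBMC or LRS will be included in the safety analysis".

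**Tests.** Section 9.2 compares adverse events with Fisher's exact test. Laboratory and vital-sign data get shift tables, and an ANCOVA of change from baseline to the highest value after administration. Crossover, period, sequence and a second baseline are not mentioned.

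**Crossover and baseline.** All subjects switch at Day 90 (9.1). For LVEF, patients are to be "evaluated for change from the new baseline (day 90 after the initial phase) to day 90 post new infusion". The exploratory endpoints, which include troponin, have the same Day 90 baseline. The safety endpoint says only: "After the crossover phase all patients will be evaluated at days 30, 60, and 90 days post the new infusion". Section 8.2.1 uses a single start of treatment for adverse events: "those occurring after initiation of treatment will be recorded as treatment-emergent". An Appendix A footnote takes one test before infusion to establish baseline, but the table row it belongs to is not visible in the text available. Appendix A also places the Holter recording and the lymphocyte sample before infusion. The Day 90 list in 7.3 states that order only for the skin test.

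**The concern.** Safety is the primary objective. Until Day 90 the randomised group and the treatment received coincide, apart from dosing errors. After Day 90 every subject has had both infusions and the two labels give different tables.

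- **By randomised group to Day 180**, the comparison is cells-then-LRS against LRS-then-cells. Both arms have had cells, so a real cell effect can cancel.
- **By treatment received**, each subject appears in both columns of an unpaired test. An effect of the cells that lasts beyond Day 90 in cell-first subjects is counted under LRS.

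The reported safety difference therefore depends on a choice that 9.2 does not make.

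The ANCOVA raises a separate problem. The panel includes haemoglobin, platelets, white cells and blood pressure, where a fall can be the finding of interest. Change to the maximum largely ignores a fall at a single visit.

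**Working it through.** **Inputs.** The plan gives no safety alpha, event rate, carryover or SD, and 9.4 says the sample size has no power basis. There is no stated figure to reproduce. Assumed throughout: two-sided alpha 0.05, and independent periods within subject. Risk per 90 days on LRS (l) and on cells (c) is 10% v 40% or 5% v 20%. Carryover f is the share of the excess risk that persists into Period 2 of cell-first subjects. Group size is 10 v 10 (Synopsis, 4.1, 5.1). Because 5.2 prints 15 for placebo and 6.1 prints 15 for both groups, 15 v 15 is also shown.

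**Formulas.**
- Cell-first risk in Period 2: r = l + f(c − l).
- By randomised group to Day 180: 1 − (1 − c)(1 − r) for cell-first against 1 − (1 − l)(1 − c) for LRS-first.
- By treatment received: difference = c − (l + r)/2.

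**Worked case, 10% v 40%.** For f = 0, 0.5 and 1, r = 0.10, 0.25 and 0.40.
- Cell-first to Day 180: 1 − 0.6×0.9 = 0.46; 1 − 0.6×0.75 = 0.55; 1 − 0.6×0.6 = 0.64.
- LRS-first to Day 180: 1 − 0.9×0.6 = 0.46.
- Treatment-received difference: 0.40 − 0.10 = 0.30; 0.40 − 0.175 = 0.225; 0.40 − 0.25 = 0.15.

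Fisher results are exact. McNemar results are simulated (40,000 runs).

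| LRS v cells | Carryover | Randomised group to Day 180 | Fisher 10 v 10 rejects | Difference by treatment received | Unpaired Fisher 20 v 20 | Exact McNemar, n=20 |
|---|---|---|---|---|---|---|
| 10% v 40% | 0 | 46% v 46% | 1.3% | 30 points | 49% | 44% |
| | 50% | 55% v 46% | 2.0% | 22.5 | 25% | 22% |
| | 100% | 64% v 46% | 4.5% | 15 | 10% | 9% |
| 5% v 20% | 0 | 24% v 24% | 1.0% | 15 | 17% | 9% |
| | 50% | 30% v 24% | 1.5% | 11.3 | 9% | 5% |
| | 100% | 36% v 24% | 2.7% | 7.5 | 5% | 3% |

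**Period 1 only.** This is free of carryover but weak.
- 10 v 10: power is 15% (10% v 40%) and 2% (5% v 20%). Five events against none gives p = 0.033; four against none gives p = 0.087.
- 15 v 15: power is 33% and 8%.
- Against the pooled unpaired test at 10 v 10, Period 1 has more power only above about 80% carryover in the first case, and never in the second.
- At 15 v 15 the crossing points are about 60% and about 75%. Pooled 30 v 30 power at 50% and 75% carryover is 39% and 25% in the first case, and 12.1% and 8.3% in the second.

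**Maximum against minimum.** Simulated baseline-adjusted ANCOVA, 10 v 10, three post-infusion visits, 2 SD fall in treated subjects, correlation between visits 0.3, 0.5 and 0.7.
- All treated subjects fall at one visit: maximum 8.9%, 8.8%, 7.6%; minimum 89.5%, 95.5%, 99.6%. Repeat runs put the maximum at about 7 to 9%.
- Half fall at one visit: about 6% on the maximum; about 27 to 45% on the minimum, depending on the correlation and on how the affected subjects are assigned.
- A fifth fall at one visit: about 5% against about 7 to 11%.
- All fall at two visits: about 30 to 38% on the maximum. At all three visits: over 99%.

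**The case against.** The strongest reply is that the grouping is already settled. The introduction to Section 9 covers every safety table and specifies actual treatment; the Synopsis agrees. The label in 9.2 may be loose wording for treatment group. The analyses are called descriptive, a detailed SAP is promised, the DSMB receives all serious events, and the stopping rules do not depend on these tests.

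Much of this stands, and it rules out several stronger readings:

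- A reader might infer that the plan has chosen randomised group to Day 180. Two passages point the other way, so 46% v 46% shows what following the 9.2 label literally would do; it does not predict the analysis.
- A reader might infer that safety data have no second baseline at all. Troponin has one as an exploratory biomarker, and the Appendix A footnote supplies one for a test that cannot be identified. The gap covers most other laboratory tests and vital signs.
- A reader might infer that the ANCOVA misses falls in general. It is insensitive to a fall at a single visit, much less so at two, and not at all at three. Shift tables and descriptive minima may also show falls, and clinically significant abnormalities needing active management are recorded as adverse events (8.2.3 d).
- A reader might infer that the unpaired test is the main fault. In these scenarios Fisher and McNemar power differ by only about 2 to 7 points.

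What the reply does not answer is the period. As-treated grouping does not say whether Period 1, Period 2 or both enter the tests, nor where late events after cells belong. Section 9.2 prescribes two between-group tests, and even descriptive tables need defined columns. An SAP written before analysis is not necessarily written before data are seen in a single-blind trial with ongoing safety review.

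**Conclusion.** The point holds and should be fixed before data are seen. The 9.2 label conflicts with two passages that support treatment received. The period for the comparisons and the placing of events after Day 90 in cell-first subjects are not stated. Most laboratory tests and vital signs lack a stated Period 2 baseline.

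Under the assumed 10% v 40%, the same risks without carryover give a difference of 0 or 30 points according to grouping. The as-treated difference halves to 15 points if the effect carries over fully. The maximum-only ANCOVA is a separate and narrower weakness, confined mainly to falls at a single visit.

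The sizes rest on assumed event rates, carryover, effect size, visit correlation and alpha. Power also depends on a group size that the plan prints inconsistently. Naming Period 1 as the carryover-free comparison is a trade-off: it removes carryover bias and, in most of these scenarios, costs power. Tabulating by sequence and period without formal tests would also be defensible.

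**What to change.** In Section 9.2:

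1. Replace the grouping label with treatment received, in line with the Section 9 introduction and the Synopsis.
2. Tabulate all safety data by sequence and period in three columns: LRS before any cells, after cells, and LRS after prior cells. Assign adverse events to the period of onset. Never pool the third column with cell-naive LRS.
3. State that the between-group comparison free of carryover is the Period 1 data. Any comparison pooled over periods is supportive and uses a paired method such as exact McNemar.
4. For Period 2 laboratory tests and vital signs, report change from both the pre-study baseline and the pre-infusion Day 90 value. A Day 90 baseline alone would set a persistent shift after cells to zero. State in 7.3 and Appendix A that these Day 90 measurements precede the infusion.
5. Analyse change to the minimum as well as the maximum, using both where either direction matters, such as white cells and blood pressure.

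Reconcile the group sizes in 5.2 and 6.1 with the rest of the protocol.

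**Cost.** Protocol and SAP wording, table shells and one sequencing line. No new assessment is needed if Day 90 measurements already precede the infusion. The downside is the low Period 1 power shown above. The descriptive cells column still keeps all planned exposures: with no events in 20, the one-sided 95% upper limit is 1 − 0.05^(1/20) = 13.9%, against 25.9% for none in 10. Dropout or a positive skin test (Appendix C) would reduce these numbers; with 17 treated the limit is 16.2%.

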#### STUDY TREATMENT

Study subjects will receive infusion at two study sites under the supervision of the site Principal Investigator or qualified co-investigator. Study product administration will be performed  $7 \pm 3$  days after randomization.

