## 5.1 Subject Selection

The study will enroll a minimum of 20 subjects and will consist of 2 cohorts. Enrolled subjects will be randomized at 1:1 into an experimental group (n=10) or a placebo group (n=10). Subjects in the experimental group will receive 1.5 million cells per kg and subjects in the placebo group will receive 1 mL/kg Lactated Ringer's Solution. At 90 days the two groups will change arms and the placebo group will receive the stem cell infusion also and the initially treated group will receive a LRS at a volume of 1 mL/kg.

Eligibility will be determined by the inclusion and exclusion criteria listed below.

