## **6** INVESTIGATIONAL PRODUCT

## 6.1 Formulation, Packaging, Preparation, Randomization of aMBMC or Placebo

The study will enroll a minimum of 20 subjects and will consist of 2 cohorts. Enrolled subjects will be randomized at 1:1 into an experimental group (n=15) or a placebo group (n=15). Subjects in the experimental group will receive 1.5 million cells per kg and subjects in the placebo group will receive 1 mL/kg Lactated Ringer's Solution.

Once the subject is randomized into one of the two cohorts, the cells or placebo will be prepared. Within 8 hours of infusion, the appropriate number of cells will be thawed at the study site pharmacy and re-suspended in Lactated Ringer's Solution (LRS) at a concentration of 1x10^6 cells/mL Subjects in placebo group will receive LRS at a volume of 1 mL/kg. The study solution (cells or placebo) will be labeled to indicate that it is an investigational agent and will contain a subject's information, date, and time of formulation.

After discharge, subjects will have safety and efficacy evaluations as per Appendix A.

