## 8.2.2 Assessment of Adverse Events

Investigators will seek information on AEs and SAEs at each subject contact by specific questioning and, as appropriate, by examination. All AEs and SAEs, whether spontaneously reported by the subject or noted by authorized study personnel, will be recorded in the subject's medical record and on the appropriate AE or SAE CRF page.

Each recorded AE or SAE will be described by its duration (i.e., start and end dates), severity, regulatory seriousness criteria if applicable, suspected relationship to the investigational product, and actions taken.

Note: The investigator's assessment of causality for individual AE reports is part of the study documentation process. Regardless of the "Yes" or "No" causality assessment for individual AE reports, the sponsor will promptly evaluate all reported SAEs against cumulative product experience to identify and expeditiously communicate possible new safety findings to investigators and applicable regulatory authorities. Attribution of SAEs will be reviewed on an ongoing basis, and may be changed as additional clinical data emerge (e.g., reversibility of AE, new clinical findings in subject with AE, effects of retreatment, AEs in other subjects).

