#### 9.3 Efficacy Analyses

The actual score and calculated change from baseline for each outcome measure (LV end diastolic volume, LVEF, Ventricular Arrhythmias, Kansas City Cardiomyopathy Questionnaire and the New York Heart Association Classification) will be tabulated for each scheduled assessment visit. Summary statistics will consist of sample size (N), means, standard deviations, medians, and minimum and maximum values will be used to summarize the data. Subjects who receive complete dose of investigational product or LRS and have post-administration assessments will be used as the efficacy evaluable population for statistical analysis.

The primary efficacy endpoint will be evaluated and is the change from baseline to Day 90, and 180 on the above measures. For each of the efficacy endpoints, a mixed-effect repeated measures (MMRM) analysis will be conducted to determine if the change from baseline to six months in the experimental group is different than that for the placebo group. The model will include the change in endpoint score from baseline to each post-baseline visit as the outcome variable, the baseline score, time, study site, treatment group and time-by-treatment interaction as fixed effects, and participant as a random effect. An unstructured covariance matrix will be used to model the within-subject variance-covariance errors. Time (0, 30d, 90d, and 180d) will be treated as a categorical variable in the analysis. The mixed model seamlessly accommodates different times of measurement as well as missed measurement and data from participants who are lost to follow up.

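### Allocation is stratified by site and the efficacy model includes site, but the adverse-event comparison in 9.2 is an unstratified Fisher's exact test, which is valid but can lose some power if event rates differ by site

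*Combined protocol and SAP*

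**What the plan says.** Section 9.1 states that "participants will be randomly assigned to the experimental or placebo group in a 1:1 allocation ratio, stratified by site". The synopsis (Study Treatment) says "Study subjects will receive infusion at two study sites", so there are two strata.

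Section 9.3 fits a mixed model to the efficacy endpoints with "the baseline score, time, study site, treatment group and time-by-treatment interaction as fixed effects". The stratification factor is therefore carried into the efficacy analysis.

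Section 9.2 is the primary safety analysis. It presents adverse-event incidence by grade, system organ class and preferred term, and "by relationship of the adverse events to the study treatment and compared using a Fisher's Exact Test". It names no stratification. Laboratory and vital-sign changes are compared by ANCOVA, with no covariates listed.

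Three other statements bear on the point. The opening of Section 9 calls the analyses descriptive, tabulates by treatment actually received, and promises a detailed SAP before data analysis. Section 9.4 says the sample size was not set by power. Section 9.1 also has every subject switch product at 90 days, and 9.2 does not say whether its tests cover the first period or both.

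**The concern.** Fisher's test on a single 2x2 table has no place for site. If the underlying event rate differs between sites, a test that ignores site treats that difference as chance variation, although allocation within site has already balanced it between arms. The test then rejects less often than its nominal level allows, both when there is no effect and when there is harm.

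Some difference between sites is plausible. Section 8.2.2 says "Investigators will seek information on AEs and SAEs at each subject contact by specific questioning", so capture depends partly on the staff who ask. Safety is the primary objective and the arms are small, so sensitivity is scarce. It is also odd that the plan uses its stratification factor for the secondary objective and not for the primary one, without giving a reason.

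**Working it through.** **Inputs from the documents.** Two sites (synopsis, Study Treatment); 1:1 allocation stratified by site (9.1); 10 per arm (5.1). Section 6.1 gives 15 per arm and 5.2 mixes the two figures. These passages must be reconciled; 10 is the base case here and 15 a sensitivity case.

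**Inputs assumed, because the documents give none.** First-period comparison; two-sided 0.05; balance within site, at 5+5, 7+3 or 8+2 subjects per arm; event rates by site and arm. Where an odds ratio (OR) is used, cell rate = OR x odds / (1 + OR x odds), with odds = p/(1-p) for the LRS rate p. For example, at OR 10 an LRS rate of 10% gives 1.111/2.111 = 53%.

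The plan states no power or event rate, so there is no figure of its own to reproduce.

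**Method.** Every possible table was enumerated. The unstratified test refers the cell-arm event count to one hypergeometric distribution. The stratified test refers the same count to the convolution of the two site-specific hypergeometric distributions, given each site's event total.

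**One example by hand.** Take 7/10 events on cells and 2/10 on LRS, made up of 2/5 vs 0/5 at site A and 5/5 vs 2/5 at site B.
- Unstratified: 9 events among 20. P(7) + P(8) + P(9) = (120x45 + 45x10 + 10x1)/167960 = 5860/167960 = 0.0349. The opposite tail is equal, so p = 0.070.
- Stratified: at A, P(both events on cells) = 10/45 = 0.222. At B, P(5 of 7 on cells) = 10/120 = 0.0833. The product is 0.0185. The opposite extreme is equal, so p = 0.037.

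**Power, 10 vs 10, 5+5 per arm (%).**

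| LRS rate by site | Cell rate by site | Fisher | Stratified | Gain |
|---|---|---|---|---|
| 10 / 10 | 30 / 30 | 5.7 | 6.1 | 0.4 |
| 10 / 10 | 50 / 50 | 29.5 | 30.2 | 0.7 |
| 20 / 20 | 71 / 71 (OR 10) | 45.4 | 46.1 | 0.7 |
| 15 / 25 | 35 / 50 (OR 3) | 7.0 | 7.6 | 0.6 |
| 15 / 25 | 64 / 77 (OR 10) | 43.1 | 44.5 | 1.4 |
| 15 / 5 | 60 / 40 | 29.1 | 30.9 | 1.8 |
| 10 / 40 | 25 / 67 (OR 3) | 4.6 | 7.1 | 2.5 |
| 10 / 40 | 53 / 87 (OR 10) | 30.4 | 37.3 | 6.9 |
| 10 / 60 | 53 / 94 (OR 10) | 17.7 | 28.7 | 11.0 |
| 20 / 0 | 80 / 20 | 26.6 | 42.4 | 15.8 |

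**Other splits.** With equal site rates the gain reaches at most 1.7 points (8+2, 10% vs 70%). For LRS 15/5 and cells 60/40 it is 1.2 points at 7+3 (31.2 to 32.4) and 3.5 at 8+2 (32.3 to 35.8). The last figure is the one case found above 2.5 points with LRS rates 10 points apart at 10 per arm.

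**15 vs 15 (8+7 per arm).** 10% vs 50% at both sites: 53.6 to 54.9. LRS 15/5 and cells 60/40: 53.7 to 57.8.

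**Type I error.** With both arms at 50% and 10% by site, Fisher rejects 0.6% of the time and the stratified test 1.5% (5+5), or 0.8% and 1.9% (8+2). Both are far below 5%.

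**ANCOVA.** With 20 subjects, intercept, treatment and baseline leave 17 degrees of freedom; adding site leaves 16. If R2 is the share of residual variance that site explains, the interval-width ratio is t(0.975,16) x sqrt(1-R2) / t(0.975,17).
- R2 = 0: 2.120/2.110 = 1.005.
- R2 = 0.10: 0.953.
- R2 = 0.30: 0.841.

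The R2 values are assumptions.

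**The case against.** The strongest reply is that little turns on this. The analyses are called descriptive, no decision rule attaches to the Fisher p-values, and neither the stopping rules (8.5) nor the DSMB provisions (8.6) refer to them. The large gains need very large site differences together with a large effect. At an odds ratio of 3 with modest site differences, power is below 8% with either test. With no events on LRS, five of ten on cells are needed to reach p < 0.05 (p = 0.033). Sample size, not site adjustment, is the main limit. All of this stands and sets the weight of the point. It does not remove the mismatch, because 9.2 still commits to a named comparative test.

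A reader might infer more than the documents support:
- **That the test does lose power, or that uncertainty is wider.** No site-specific event rate is given, and with equal site rates the gain is only a fraction of a point to 1.7 points. No interval for an adverse-event difference is planned, and with equal rates the standard error of the risk difference is unchanged.
- **That the sites use different questioning methods.** Section 8.2.2 sets one instruction for all investigators. A site difference is plausible but not documented.
- **That site is excluded from the ANCOVA.** Section 9.2 lists no covariates, which is silence and not a stated exclusion.

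The crossover objection also has force. If 9.2 is meant to pool both periods by treatment received, the same subjects appear on both sides. Independence then fails for Fisher's test and for the site-stratified test alike. The recommendation is therefore limited to the first period.

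**Conclusion.** The mismatch between 9.1, 9.3 and 9.2 is in the text. Its effect runs in one direction: the unstratified test keeps its type I error but is conservative when event rates differ by site, so it can miss some excess of events on cells.

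At 10 per arm, the power recovered by stratifying is about 0.5 to 2.5 points when site rates are equal or about 10 points apart. It is a little less when overall power is very low, and 3.5 points in one lopsided split. It is about 6 to 11 points when LRS rates are 30 to 50 points apart with an odds ratio of 10. These figures rest on assumed rates, balance within site and a first-period comparison. Stratifying lost power in none of the scenarios run. This is a worthwhile refinement to settle before data are seen, not an error that invalidates the safety analysis.

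**What to change.** In Section 9.2, and in the SAP still to be written:
1. State that the randomised adverse-event comparison uses the first period (before crossover) and is made with a site-stratified exact test (conditional Mantel-Haenszel) in place of Fisher's test.
2. State that the laboratory and vital-sign ANCOVA includes site and baseline, as the 9.3 model does.
3. State that any comparison using data from both periods will use a within-subject method.

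If the sponsor prefers to keep the unstratified test, the SAP should say so and give the reason.

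The cost is a few sentences and standard software, with no new data. The ANCOVA gives up one degree of freedom, which makes its interval about 0.5% wider if site has no effect.
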